After informed consent is obtained, patients will be assigned to either a treatment group or a standard care group. Because of the nature of the treatment blinding is not possible. Patients will be informed of their group assignement when they arrive on the floor after surgery. Each patient in the treatment group will receive ${\rm HBO}_2$ treatments in the Duke Center for Hyperbaric Medicine and Environmental Physiology using normal treatment protocols already established and approved by DUHS for the administration of HBO $_2$. Treatments will be given twice per day until the patient is discharged or 10 treatments are given.

Treatments will consist of breathing 100% O $_2$ through a head tent while inside a hyperbaric chamber at 2 ATA for 2 hours. Hyperbaric chambers at Duke allow for the presence of nursing staff and emergency access into the chamber while treatment is ongoing. Patients will experience a 15 minute compression and 5 minute decompression phase.

The Vascular Quality Initiative (VQI) is a multicenter voluntary reporting system for outcomes related to vascular surgery. The primary outcome of this study, postoperative complications, will be those outcomes meeting the definition set out in the VQI data dictionary, the set of definitions for inclusion in the VQI databse. This allows for a standard definition of complications recognized by a majority of academic medical centers across the country.

Secondary outcomes will include: Hospital length of stay, 90-day mortality, failure to heal at 4 and 8 week follow-up visits and ability to ambulate with a prosthesis at 6 months post amputation. Patients will be examined daily during their inpatient stay and then at 4 and 8 week follow-up visits once discharged from the hospital. Periwound transcutaneous oxygen presures will be taken prior to administration of HBO₂ and at the completion of 10 treamtents.

The statistical plan for this study will test non-directional hypotheses (two-sided tests). Bonferroni correction will be used to adjust for multiple tests. SAS 9.4 (SAS Institute, Inc.) will be used to analyze the data. The main analysis of the primary efficacy hypotheses will include data from all randomized patients in the group to which random assignment is made. Hence, the analysis will be intention to treat, and regardless of subsequent events and every effort will be made to continue to follow all patients that begin the study.

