The statistical plan for this study will test non-directional hypotheses (two-sided tests). Bonferroni correction will be used to adjust for multiple tests. SAS 9.4 (SAS Institute, Inc.) will be used to analyze the data. The main analysis of the primary efficacy hypotheses will include data from all randomized patients in the group to which random assignment is made. Hence, the analysis will be intention to treat, and regardless of subsequent events and every effort will be made to continue to follow all patients that begin the study.

Proportions and differences in proportions in the difference complication rate requiring reoperation in 30 days will be estimated along with 95% confidence interval. The difference in reoperation rates will be examined using Z-test. The analysis is similar for secondary outcomes. Exploratory outcome of 90-day mortality in the two treatment groups will be determined using Kaplan-Meier techniques with log-rank test. The Cox proportional hazards model will be used to determine the predictors of survival. Model assumptions will be examined and goodness of fit of these models will be assessed.

Based on randomized control trials of ${\rm HBO}_2$ effects on healing diabetic foot ulcers this study is proposed to achieve 80% power to detect an effect size of 0.62, or reduction of complications by 60% by randomizing 40 subjects into each of the treatment and placebo groups. Hence, 80 subjects will be needed for this study. Given the high volume of operations conducted at Duke this should be achievable in less than 3 years.	
Data & Safety Monitoring	
 Summarize safety concerns, and describe the methods to monitor research subjects and their data to ensure their safety, including who will monitor the data, and the frequency of such monitoring. If a data monitoring committee will be used, describe its operation, including stopping rules and frequency of review, and if it is independent of the sponsor (per 45 CFR 46.111(a) (6)). Clinical and demographic data will be collected electronically and stored using Duke University's Redcap system. Information pertaining to blinding, patient treatment, or any other study information that may arise incidentally will be stored in the Duke hyperbaric treatment facility in a locked cabinet in the nurse manager's office. 	
Privacy, Data Storage & Confidentiality	
Complete the Privacy and Confidentiality section of the iRIS submission form.	
Study Scope	

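### Bonferroni is promised without a defined family or per-test alpha, while the 80% power statement fits only one uncorrected two-sided test at 0.05

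*Combined protocol and SAP*

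**What the plan says.** The multiplicity rule is one sentence, "Bonferroni correction will be used to adjust for multiple tests", which appears in the Research Abstract, in Design & Procedures and in Data Analysis & Statistical Considerations. In all three places it follows a statement that tests are two-sided. None of them says how many tests are meant, which outcomes form the family, or what alpha each test receives.

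Design & Procedures names one primary outcome, postoperative complications as defined by the Vascular Quality Initiative. It then lists the others: "Secondary outcomes will include: Hospital length of stay, 90-day mortality, failure to heal at 4 and 8 week follow-up visits and ability to ambulate". The last of these refers to prosthetic walking, judged six months after surgery. Counting healing at 4 and at 8 weeks separately, that is five secondary comparisons. The analysis text says that secondary outcomes are analysed in a similar way, and there it labels 90-day mortality exploratory.

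The sample size paragraph in Data Analysis & Statistical Considerations claims "80% power to detect an effect size of 0.62, or reduction of complications by 60" per cent, with 40 patients in each arm, and concludes "Hence, 80 subjects will be needed for this study". It states no alpha and does not mention the correction. The difference in proportions "will be estimated along with 95% confidence interval", with no adjustment mentioned. Design & Procedures also mentions a possible midpoint analysis.

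**The concern.** The decision rule and the sample size justification should describe the same test. Here the rule promises a correction, and the power figure looks like that of a test without one. Nothing places the primary outcome outside the family, and the intention-to-treat sentence even refers to primary efficacy hypotheses in the plural. A statistician writing the analysis program could not tell from the text whether the primary p-value is to be compared with 0.05, 0.01 or 0.0083.

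Two things are at stake. First, if the primary shares alpha with the secondaries, it loses a substantial part of its power to outcomes that could be protected in another way. Second, the threshold for the main conclusion is left open in a trial where blinding is not possible, so it could be settled after results are visible.

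**Working it through.** **Inputs**

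- Effect size d = 0.62, n = 40 per arm, target power 80%: Data Analysis & Statistical Considerations.
- Two-sided tests: same section.
- Family-level alpha 0.05: **assumed**. The plan does not state it. It agrees with the 95% interval and reproduces the stated power.
- Dropout: none stated, none applied.
- Number of tests k: not stated, so varied.

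**Step 1. Reproduce the plan's figure (k = 1).**

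Power = Φ(d·√(n/2) − z₁₋α/₂). With d·√(n/2) = 0.62 × √20 = 2.773 and z = 1.960, power = Φ(0.813) = 79.2%.

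The matching sample size is 2(z₁₋α/₂ + z₀.₈₀)²/d² = 2(1.960 + 0.842)²/0.3844, which rounds up to 41 per arm. Both results agree with the plan to within rounding. A one-sided test at 0.05 would give 87.0% and 33 per arm, which does not match. The stated 80% is therefore the power of one two-sided test at 0.05.

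**Step 2. Apply Bonferroni with the primary inside a family of k tests.**

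Replace α by 0.05/k and keep everything else.

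| k | Reading | Alpha per test | Power at 0.62, n = 40 | n per arm for 80% |
|---|---|---|---|---|
| 1 | Correction covers secondaries only | 0.05 | 79.2% | 41 |
| 2 | Smallest family with the primary in it | 0.025 | 70.2% | 50 |
| 4 | Mortality exploratory, healing counted once | 0.0125 | 60.8% | 59 |
| 5 | Mortality exploratory | 0.01 | 57.8% | 61 |
| 6 | All named outcomes | 0.00833 | 55.3% | 64 |

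Example for k = 6: z = 2.638, and Φ(2.773 − 2.638) = Φ(0.134) = 55.3%.

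**Step 3. Check that the result does not depend on the formula.**

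The plan does not say what kind of effect size 0.62 is. A t-test gives 78.2% (k = 1), 68.7% (k = 2), 55.5% (k = 5) and 52.9% (k = 6). If 0.62 is read as Cohen's h, a 60% reduction corresponds to 47.6% v 19.1%. A pooled two-proportion test at those rates gives 78.5%, 68.9%, 55.6% and 53.0%. The pattern is the same on each version.

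**Step 4. Size of the gap.**

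The smallest loss, with k = 2, is 79.2 − 70.2 = 9.0 points. With all six outcomes it is 79.2 − 55.3 = 23.9 points, and restoring 80% would take 128 patients (64 per arm) before any dropout.

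**The case against.** The strongest reply is that the documents never state a six-test family. The plan names a single primary outcome and labels the rest secondary, so one natural reading is that the correction governs only the secondaries. On that reading the primary keeps about 79% and the power statement is coherent. The close fit of 80% to a single test at 0.05 supports this reading as well as it supports an oversight. Six is also the highest count of the named outcomes, because the analysis text calls mortality exploratory. All of this stands, and the lower power figures are therefore conditional. It does not remove the gap, because the plan does not say that the primary is exempt.

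A second reply is that Bonferroni is conservative, so validity is not threatened. That also stands: nothing in the Bonferroni rule itself inflates type I error. The defect is in prespecification and in the power claim.

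Two further inferences are tempting and should not be drawn.

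- **Contradictory verdicts.** A reader might infer that the unadjusted 95% interval will contradict the corrected test. The plan uses the interval for estimation and the Z-test for the decision, and does not make the interval a success criterion. The chance of such a split is essentially the power difference again.
- **Low power at the local event rate.** A reader might take the 27/98 complication rate in Background & Significance and attribute the resulting low power to multiplicity. At that rate a 60% reduction gives only about 48% power at 0.05 with no correction at all. That is a separate mismatch between 0.62 and a 60% reduction.

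**Conclusion.** The point holds in conditional form. The Bonferroni family and the per-test alpha are undefined, and the 80% power statement takes no account of the promised correction. Power for the primary test at the plan's own effect size lies anywhere from about 79% (correction limited to the secondaries) to 55.3% (all six outcomes), with 57.8% if mortality is left out. Any family of two or more that includes the primary falls at least 9 points short of the single-test figure.

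A reader might conclude that the trial simply has 55% power. The documents do not support that, since it needs a six-outcome family that they never state.

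The figures assume a family-level alpha of 0.05 two-sided, 40 evaluable patients per arm, an effect size of 0.62 taken at face value, and no alpha spent at the midpoint analysis.

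**What to change.** Replace the Bonferroni sentence in the Research Abstract, Design & Procedures and Data Analysis & Statistical Considerations with a rule along these lines:

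1. The primary outcome, named as one specific comparison, is tested first at two-sided 0.05 without sharing alpha with the secondaries, and is reported with its matching 95% interval.
2. If it is significant, the listed secondary outcomes are tested by Holm's step-down procedure at family level 0.05. If not, they are reported as supportive, with 95% intervals.
3. State whether 90-day mortality is in the secondary family or exploratory.
4. State that the 0.62 power calculation assumes one two-sided test at 0.05 (about 79%). If the sponsor prefers to keep the primary in the Bonferroni family, define that family and restate power as about 55–58%, or re-size (61 per arm for five tests, 64 for six).
5. If the midpoint analysis includes an efficacy test, account for it in the primary alpha. Testing at a full 0.05 at both looks would inflate the type I error.

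The first route costs wording only. It controls the family-wise error at 0.05, and over the same set of secondaries Holm rejects everything that Bonferroni would. The small downside is that secondary claims depend on the primary succeeding. The change does not resolve the mismatch between an effect size of 0.62 and a 60% reduction from 27/98, and item 4 should not be read as endorsing 80% power at that rate.
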